## 4. Data Collection & Outcome Measures

Primary vs. Secondary Outcome Measures

### **Primary Outcome Measure:**

Improvement in blastocyst formation rate following oPRP treatments, as assessed by the use of a time-lapse incubator in conjunction with AI.

### **Secondary Outcome Measures:**

Improvement in embryo quality based on Morphokinetics using the AI score from time-lapse videography.

Changes in ovarian reserve markers (AMH, AFC, FSH, E2) post-oPRP.

Increase in the number of mature (MII) oocytes retrieved in the second IVF cycle.

Increase in 2 PN embryos formed

Increase in Day 3 embryos formed with 6 cells or more

Increase in Blastocysts formed

Increase in High Quality blastocysts formed (3BB or better)

Increase in Euploid embryos based on PGT-A analysis when available

Clinical pregnancy rate per embryo transfer.

Live birth rate following embryo transfer.

### **MONITORING & SAFETY**

Patients will be closely monitored throughout both IVF cycles to ensure optimal response and minimize risks.

Bloodwork and ultrasound assessments will be conducted regularly to track follicular development, endometrial thickness, and hormonal response.

Any adverse events, including ovarian hyperstimulation syndrome (OHSS), infection, or complications related to IVF or oPRP injections, will be documented and reported.

Safety data from over 940 oPRP injections performed to date at GNF since July 2021 indicate no major complications requiring hospitalization, blood or blood product transfusion, surgery, or other interventional procedures.

The most commonly reported side effect from the ovarian PRP procedure was transient pain at the ovarian injection site, lasting a maximum of four days, all of which resolved with expectant management.

### **Inclusion & Exclusion Criteria**

#### **Inclusion Criteria:**

Patients age 18 to 47 who are eligible for both In Vitro Fertilization (IVF) and ovarian Platelet-Rich Plasma (oPRP) injections.

No known contraindications to IVF or oPRP as outlined in the exclusion criteria.

Willing to undergo two consecutive IVF cycles, with the first cycle serving as a control and the second cycle including oPRP injections.

Adequate ovarian reserve based on baseline antral follicle count (AFC) and anti-Müllerian hormone (AMH) levels.

#### **Exclusion Criteria:**

Patients will be excluded from participation if they meet any of the following conditions:

Anovulation due to perimenopause or menopause, as determined by clinical evaluation and laboratory testing

Ovarian accessibility issues, including:

Ovaries not accessible via transvaginal ultrasound  
Large unresolved ovarian cysts  
History of ovarian abscess or pelvic infection  
Any medical condition where pregnancy is contraindicated, including but not limited to:  
Severe cardiovascular disease  
Uncontrolled hypertension or diabetes  
Renal or hepatic insufficiency  
History of malignancies, including:  
Breast, gynecologic, hematologic (leukemia, lymphoma), or other cancers  
Borderline ovarian tumors  
Hematologic disorders, including:  
Anemia (low hemoglobin/hematocrit levels)  
Sickle cell disease, beta-thalassemia, or alpha-thalassemia  
Polycythemia (abnormal increase in red blood cells)  
Thrombocytopenia (low platelet count) or any platelet dysfunction disorder  
Hypercoagulable conditions, such as:  
Deep vein thrombosis (DVT)  
Pulmonary embolism (PE)  
History of stroke or transient ischemic attack (TIA)  
Uncontrolled or poorly managed autoimmune diseases, including:  
Systemic lupus erythematosus (SLE)  
Sjögren's syndrome  
Uncontrolled diabetes mellitus  
Severe uncontrolled thyroid dysfunction (hypothyroidism or hyperthyroidism)  
Use of medications contraindicated for IVF or oPRP, including:  
NSAIDs (Non-Steroidal Anti-Inflammatory Drugs)  
Anticoagulants or blood thinners (oral or injectable, e.g., Lovenox, Heparin, Warfarin)  
Chronic corticosteroid use  
Substance use that may negatively impact IVF or oPRP response, including:  
Excessive alcohol consumption  
Recreational drug use  
Prior oPRP treatment within the past 6 months  
Patients unwilling or unable to complete two consecutive IVF cycles  
Patients under the age of 18 or over the age 47

#### NUMBER OF SUBJECTS / LENGTH OF PARTICIPATION

This study employs a prospective non-randomized self-controlled design, where each patient serves as their own control by undergoing two IVF cycles—one without oPRP (control cycle) and one following two oPRP treatments (study cycle). While this design reduces inter-patient variability, we acknowledge the potential for time-dependent confounders and variations in ovarian response.

Baseline Blastocyst Formation Rate per Oocyte Retrieved: 25% (based on retrospective

clinical data).

Expected Improvement of Blastocyst formation rate with oPRP: 35% (a 10% absolute increase, representing a 40% relative improvement).

Statistical Parameters:

Power: 80%

Alpha (Significance Level): 0.05

Study Design: Self-controlled (paired analysis)

Based on these parameters, we aim to detect a minimum detectable effect size of approximately a 10% absolute increase in blastocyst formation rate (from 25% to 35%). To achieve this, a total sample size of 180 patients is required. This calculation accounts for the paired nature of the study design and the expected discordant proportions between the control and study cycles.

To maintain statistical robustness, we have chosen a sample size of 180 patients, which includes an estimated 10-15% dropout rate for cycle cancellations or variability in ovarian response. An interim analysis will be conducted at 50% enrollment to validate initial assumptions regarding oPRP's impact on blastocyst formation.

This study will also consider an external control group of patients undergoing two IVF cycles without oPRP to further validate findings and minimize bias.

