## 2. First IVF Cycle (Control)

The first IVF cycle will serve as a control cycle, conducted without oPRP injections.

The ovarian stimulation protocol (natural, mild, or conventional) will be determined based on AFC and hormonal profile.

Once the lead follicle reaches the appropriate size ( $\geq 18$  mm), ovulation will be induced using 10,000 IU of human chorionic gonadotropin (hCG) or 250 mcg Ovidrel®, or 80-100 IU of Leuprolide acetate or a combination of the above administered approximately 35.5 hours prior to retrieval.

Oocyte retrieval will be performed under deep intravenous (IV) sedation by a board-certified anesthesiologist, using transvaginal ultrasound guidance.

Fertilization Method Options:

Conventional Insemination

Intracytoplasmic sperm injection (ICSI)

ICSI + Zymot sperm selection

ICSI + Zymot + Physiological ICSI (PICSI)

With or without PGT-A using SNP-based LifeView® technology from Genomic Prediction LLC.

Up to 15 embryos will be cultured in the time-lapse incubator, which in conjunction with AI, provides an automated embryo quality score based on morphokinetic parameters. The resulting AI Score will not be used to guide any clinical decisions.

All embryos reaching the blastocyst stage will be biopsied (if PGT-A is elected), vitrified, and stored for potential future embryo transfer.

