## 3. oPRP Treatment & Second IVF Cycle (Study Cycle)

Following the first IVF cycle, patients will undergo their first oPRP injection:

Timing: 1-2 weeks after the onset of the next menstrual cycle.

Procedure: Under IV sedation, a patient's autologous PRP will be prepared and injected directly into both ovaries under transvaginal ultrasound guidance.

Second IVF Cycle (oPRP Study Cycle)

The same ovarian stimulation protocol will be used for consistency.

A second oPRP injection will be performed on stimulation days 2-5 to enhance folliculogenesis.

Ovulation will be triggered at the same follicular size thresholds, and oocyte retrieval will follow identical protocols.

Fertilization methodology will be identical to the first cycle unless no fertilization is identified in the first cycle.

Embryo Development Analysis: Up to 15 embryos will be cultured in a time-lapse incubator, which in conjunction with AI, provides an automated embryo quality score based on morphokinetic parameters. The resulting AI Score will not be used to guide any clinical decisions.

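### The sample size of 180 rests on discordant proportions, which a blastocyst rate over several oocytes per cycle does not have, so the 80% power is unsupported

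*Protocol*

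**What the plan says.** The Protocol section *NUMBER OF SUBJECTS / LENGTH OF PARTICIPATION* contains the only power statement.

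- **Planning rates.** The control-cycle figure is given as "Baseline Blastocyst Formation Rate per Oocyte Retrieved: 25" per cent, taken from retrospective clinical data. The target is 35%, a rise of 10 percentage points.
- **Error rates and design.** Alpha is 0.05 with sidedness not stated, power is 80%, and the analysis is paired.
- **Basis of the 180.** "This calculation accounts for the paired nature of the study design and the expected discordant proportions between the control and study cycles". No discordant proportion is given, and no test or formula is named.
- **Dropout.** The section calls 180 the required number and also describes it as a figure "which includes an estimated 10-15% dropout rate for cycle cancellations or variability in ovarian response".

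*Primary Outcome Measure* reads "Improvement in blastocyst formation rate following oPRP treatments, as assessed by the use of a time-lapse incubator in conjunction with AI". It states no denominator; the per-oocyte unit appears only with the 25% baseline. In the control cycle, "Up to 15 embryos will be cultured in the time-lapse incubator", and the section on the study cycle sets the same ceiling of 15.

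**The concern.** A discordant proportion is the share of matched pairs whose two yes/no results differ. It needs one binary result per patient in each cycle, and the protocol defines none. Its endpoint is a fraction: blastocysts over oocytes, or over embryos, in a cycle. A patient may contribute many units per cycle, and no oocyte or embryo from the first cycle has a partner in the second. The mismatch holds with either denominator.

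A discordant-proportion formula also has no term for the number of oocytes per cycle, although yield largely sets the precision of a per-oocyte rate. The quantity that governs power, the spread of within-patient differences in the rate, does not enter the stated justification. A reader cannot tell whether the trial is comfortably powered or short.

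**Working it through.** **Inputs.** From the protocol: rates 0.25 and 0.35, difference 0.10, alpha 0.05, power 80%, 180 patients, dropout 10–15%. Assumed: a two-sided test. Evaluable pairs are 180 × 0.90 = 162 and 180 × 0.85 = 153.

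**1. Can the plan's 180 be reproduced?** The wording suggests a McNemar-type calculation, with ψ the total discordant proportion:

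n = [1.96·√ψ + 0.8416·√(ψ − 0.01)]² / 0.01

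- Solving for ψ at 80% power gives 0.232 for n = 180, 0.209 for n = 162 and 0.198 for n = 153.
- With independent cycles, ψ = 0.25 × 0.65 + 0.75 × 0.35 = 0.425 and n = 331.2, rounded up to 332. This marks a reference point and is not an estimate of a shortfall.

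So 180 can be reached, but only with a ψ the protocol does not give, and only by treating the per-oocyte 25% and 35% as per-patient probabilities.

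**2. The same question on the rate scale.** For a paired difference in patient-level rates with standard deviation SD:

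- pairs needed = (2.8016 × SD / 0.10)², rounded up
- power = Φ(0.10·√n / SD − 1.96)
- detectable difference = 2.8016 × SD / √n

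| SD (assumed) | Pairs for 80% | Power, 153 pairs | Power, 162 | Power, 180 | Detectable at 153 (points) |
|---|---|---|---|---|---|
| 0.25 | 50 | >99% | >99% | >99% | 5.7 |
| 0.30 | 71 | 98% | 99% | 99% | 6.8 |
| 0.40 | 126 | 87% | 89% | 92% | 9.1 |
| 0.45 | 159 | 78% | 81% | 85% | 10.2 |
| 0.50 | 197 | 70% | 72% | 77% | 11.3 |

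The largest SD that keeps 80% power is 0.10·√n / 2.8016: 0.479 at 180 pairs, 0.454 at 162 and 0.442 at 153.

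**3. How the SD depends on yield.** With m oocytes in each cycle and a patient-by-cycle standard deviation t on the rate scale:

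SD² = Σ over p = 0.25, 0.35 of [t² + (p(1 − p) − t²)/m]

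For t = 0 this is 0.415/m. For t = 0.20 it is 0.08 + 0.335/m. Both m and t are assumptions.

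| m | SD, t = 0 | Pairs | SD, t = 0.20 | Pairs |
|---|---|---|---|---|
| 2 | 0.46 | 163 | 0.50 | 195 |
| 3 | 0.37 | 109 | 0.44 | 151 |
| 5 | 0.29 | 66 | 0.38 | 116 |
| 8 | 0.23 | 41 | 0.35 | 96 |

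Across this range the number of pairs needed varies almost fivefold, from 41 to 195, and the stated calculation contains nothing that would place the trial within it.

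**The case against.** Three points can be made for the protocol.

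**The method is inferred.** The protocol names no test, and in a loosely drafted application the phrase might only mean that the two proportions differ. That is possible, although the word used beside a paired design points to matched binary data. On the loose reading the 180 is just as unexplained, since no SD, correlation or yield supports it.

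**The missing inputs could sit in an analysis plan that is not shown.** This is fair for the inputs taken alone. It does not answer the mismatch, because the protocol itself states a basis for its sample size and that basis does not fit the endpoint stated beside it. An analysis plan would not repair that sentence.

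**The numbers mostly favour 180.** This stands. Of the eight yield scenarios above, only one needs more than 180 pairs and six need no more than 153. The 70% figure requires an SD of 0.50, which in that grid arises only at two oocytes per cycle with added patient-by-cycle variation. The inclusion criterion of adequate ovarian reserve makes such a low average yield less likely. Low yield is not excluded, however: women up to age 47 are eligible, and natural and mild stimulation are allowed. The point is therefore that the power is unsupported, and it should not be read as a claim that the trial is underpowered.

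**Conclusion.** The concern holds. The stated basis for 180 patients and 80% power requires one yes/no result per patient per cycle, while the endpoint is a rate over several units per cycle. The direction of any error is unknown. With 153 to 180 pairs, power for a 10-point rise runs from above 99% at SD 0.25 down to about 70% (153 pairs) or 77% (180 pairs) at SD 0.50. The 80% claim survives if the SD of within-patient differences is at most 0.442 to 0.454 with 153 to 162 evaluable pairs. These figures rest on a two-sided test, a normal approximation, assumed SDs and, in the yield table, equal oocyte numbers in both cycles. This should be fixed, because it is the only quantitative justification of the sample size, but the number itself may prove adequate.

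**What to change.** Keep 180 as the planned enrolment and replace the discordant-proportion sentence with a calculation for the rate endpoint. Two forms would serve:

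- a paired difference in patient-level proportions, blastocysts over oocytes retrieved; or
- an oocyte-level binomial mixed model with patient and patient-by-cycle random effects.

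State the denominator in the primary outcome. If the patient-level form is chosen, say how a cycle with no oocytes counts, since its proportion is undefined. Take the SD of the within-patient difference and the oocyte yield from the retrospective clinic data already cited for the 25%. Report the power, or the difference detectable with 80% power, at the 153 to 162 pairs left after the stated dropout, and name the same analysis as the primary test.

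The cost is one recalculation from existing data and a reworded paragraph, with no extra patients. The restated figure may be less favourable: if the clinic data give an SD above about 0.44 to 0.45, the protocol would have to state power below 80% or a detectable difference above 10 points.

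### 180 is given both as the number the listed power inputs require, with no dropout term, and as a total that already includes 10–15% dropout

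*Protocol*

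**What the plan says.** The sample-size statement is in the protocol section *Number of Subjects / Length of Participation*. The design is self-controlled: "each patient serves as their own control by undergoing two IVF cycles". The listed parameters are a control-cycle rate of 25% per oocyte retrieved, a study-cycle rate of 35%, 80% power, alpha 0.05 and a paired analysis.

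From these parameters the protocol concludes: "To achieve this, a total sample size of 180 patients is required". It then describes what went into the number: "This calculation accounts for the paired nature of the study design and the expected discordant proportions between the control and study cycles". Dropout is not mentioned there.

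The next paragraph returns to the same figure: "we have chosen a sample size of 180 patients, which includes an estimated 10-15% dropout rate for cycle cancellations or variability in ovarian response". The section gives no number of evaluable pairs, no number before the dropout allowance, no discordant proportion and no sidedness.

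**The concern.** In a self-controlled design the unit behind the power claim is the complete pair. A patient without a usable second cycle contributes no pair. The number of pairs the calculation needs and the number of patients to enrol are therefore different quantities whenever dropout is expected, and the protocol expects 10–15%.

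The protocol uses one figure for both. It first presents 180 as the result of a calculation whose listed inputs contain no dropout term, and then says the same 180 already contains the allowance. What is at stake is knowing what the trial needs. Suppose it ends with 155 complete pairs. If 180 is the enrolment, 155 lies inside the planned range. If 180 is the pair requirement, 155 is 25 short. The protocol as worded supports either answer.

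**Working it through.** **Inputs from the protocol (same section).** Rates 25% and 35%, so d = 0.10; power 80%; alpha 0.05, sidedness not stated; paired analysis; N = 180; dropout 10–15%. **Not in the protocol:** the discordant proportion ψ, or the SD of the within-patient difference.

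**Step 1. Try to reproduce 180.** For paired proportions (McNemar, normal approximation):

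n = (z_α·√ψ + z_power·√(ψ − d²))² / d²

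ψ is not given, so 180 cannot be computed forwards. With ψ assumed, two-sided n is 115.3 at 0.15, 154.6 at 0.20, 193.8 at 0.25 and 233.1 at 0.30. Solving backwards for the ψ that gives exactly 80% power:

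| Pairs | ψ, two-sided | ψ, one-sided |
|---|---|---|
| 180 | 0.232 | 0.295 |
| 162 | 0.209 | 0.265 |
| 153 | 0.198 | 0.251 |

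Each value is possible, since 25% and 35% allow ψ from 0.10 to 0.60. So 180 could be the pair requirement, or it could be the enrolment built on 153–162 pairs. The arithmetic does not choose between them.

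**Step 2. Apply the dropout allowance.**

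- If 180 is enrolled: 180 × 0.90 = 162 and 180 × 0.85 = 153 evaluable pairs. If the allowance was a mark-up instead, 180/1.10 = 163.6 and 180/1.15 = 156.5, or about 164 and 157.
- If 180 is the pair requirement: the matching enrolment is 180/0.90 = 200 to 180/0.85 = 211.8, or 212.

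The two roles of 180 differ by 180 − 162 = 18 to 180 − 153 = 27 pairs, or 20 to 32 enrolled patients. They coincide only at zero dropout, which the protocol does not assume.

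**Step 3. Is the enrolment reading feasible?** Take ψ = 0.20, two-sided (an assumption):

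n = (1.960 × 0.4472 + 0.8416 × 0.4359)² / 0.01 = (0.8765 + 0.3669)² / 0.01 = 154.6, or 155 pairs.

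Then 154.6/0.90 = 171.8 and 154.6/0.85 = 181.9, or 172 to 182 enrolled, a range that contains 180. This shows the reading is feasible; it does not prove it.

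**Step 4. The other reading, for illustration only.** Assume exactly 80% power at 180 pairs (ψ = 0.2324, two-sided) and that every dropout loses a pair. Power = Φ((d·√n − z_α·√ψ)/√(ψ − d²)):

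- n = 162: (1.2728 − 0.9448)/0.4716 = 0.696, giving 75.7%.
- n = 153: (1.2369 − 0.9448)/0.4716 = 0.620, giving 73.2%.

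One-sided, with ψ = 0.2945, the figures are 76.2% and 74.1%. If half the dropouts still give a pair, 166–171 pairs give 77–78% two-sided. These results follow from the 80%-at-180 assumption and are not evidence about this trial. With a paired t-test on per-patient rates, 153 pairs give two-sided power from 98% to 78% as an assumed SD of the difference goes from 0.30 to 0.45, so the document does not fix the power at 153 pairs.

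**The case against.** The strongest reply is that there is no contradiction. The protocol speaks of a *total* sample size, never of evaluable pairs, and the next paragraph explains that this total includes dropout. An enrolment needed to reach 80% power after expected losses can fairly be called required. The sentence on pairing and discordance does not claim to list everything the calculation covered, and Step 3 shows that the numbers work. What is left would be missing detail that a protocol may leave to the SAP.

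Much of this stands. The enrolment reading is the more charitable one, and on it the 80% power is kept. Leaving out the discordance and sidedness is not, by itself, a fault here. But the protocol ties 180 to its listed parameters and describes the calculation behind it without dropout. The charitable reading has to add an input that the description does not list, and it still leaves the number that the 80% claim rests on misstated as 180. An SAP cannot settle which of two protocol sentences is meant.

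A reader might go further and infer that the trial is underpowered at 73–76%, or that it must enrol 200–212. The documents do not support that. Those figures need 180 to be the pair requirement, which the text does not establish, and the power figures need a discordance solved backwards from that premise. They also count every dropout as a lost pair, although the allowance covers variable ovarian response as well as cancellations, and variable response need not remove a pair. The McNemar formula treats each patient as one yes/no pair, while the protocol's rates are per oocyte. Even on that reading the detectable difference would be 10.5–10.8 points, against a stated target of approximately 10.

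**Conclusion.** The point holds as an inconsistency in the sample-size statement. The listed inputs, which contain no dropout term, cannot give 180 both before and after a 10–15% allowance. As written, the number tied to the 80% power is off by 18–27 pairs in one sentence or the other. On the charitable reading, about 153–162 evaluable pairs support the 80% power and the error is limited to attaching *required* to the enrolment figure.

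No loss of power is shown, and 180 itself is not shown to be wrong. The 153–162 range assumes that the allowance is a proportion of those enrolled and that each dropout costs one pair. The 73–76% figure is illustrative only. The correction is worth making because the statement sets the trial's target and costs little to repair.

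**What to change.** State two numbers taken from the sponsor's existing calculation: the evaluable pairs required for 80% power, and the patients enrolled. Then correct the sentence that does not match.

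- **If 180 is the enrolment:** replace the statement that 180 patients are required with the evaluable-pair number the calculation gave (about 153–162), and say that 180 are enrolled to allow for 10–15% dropout. The 80% stays.
- **If the calculation gave 180 evaluable pairs:** keep enrolment at 180, delete the claim that 180 includes dropout, and restate the power or the detectable difference at the expected 153–162 pairs, using the sponsor's own discordance or SD. The illustrative figures above should not be copied into the protocol.

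The discordance or SD and the sidedness can be given here or by reference to the SAP. The cost is wording only, with no added patients, no added time and no change to study conduct.

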#### PURPOSE OF THIS RESEARCH

This is a non-randomized prospective self-controlled interventional study evaluating the impact of oPRP injections on embryo quality in patients undergoing two IVF cycles.

Participants will undergo two IVF cycles at Generation Next Fertility.

The first cycle will serve as the control (no oPRP treatment), while the second study cycle will incorporate oPRP injections.

Oocytes retrieved will undergo fertilization using one of the following methods:

Conventional Insemination

Intracytoplasmic sperm injection (ICSI)

ICSI with Zymot

ICSI with Zymot and Physiological ICSI (PICSI)

Patients may opt for Preimplantation Genetic Testing for Aneuploidy (PGT-A) through Genomic Prediction LLC's LifeView™ platform, which utilizes single nucleotide polymorphism (SNP) technology to enhance accuracy in detecting chromosomal abnormalities.

All embryos from both IVF cycles will be cultured in a time-lapse incubators for automated tracking and assessment.

Embryo quality will be measured by an AI software used in conjunction with the time-lapse incubators.

This study aims to evaluate whether ovarian platelet-rich plasma (oPRP) injections improve embryo quality in In Vitro Fertilization (IVF) cycles. Patients will undergo two IVF cycles:

First cycle (Control cycle): A standard IVF cycle with individualized ovarian stimulation protocols based on AMH, AFC and patient history and prior IVF outcomes when applicable.

Second cycle (Study cycle): Includes oPRP injections, administered:

1-2 weeks after the onset of menses following the first IVF cycle.

A second injection between stimulation days 2-5 of the second IVF cycle.

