The protocol of the second IVF cycle will be again based on the same criteria as the first IVF cycle. Embryos from both cycles will be monitored using a time-lapse incubator in conjunction with an AI software to analyze embryo development and assess Embryo Quality (EQ) scores. The study will determine if oPRP improves embryo quality and implantation potential. Each embryo will be given an EQ (embryo quality) score based on the morphokinetics of the embryos during the incubation period. The Embryo Quality (EQ) Score, generated through AI analysis, will be used to assess whether oPRP improves embryo development, viability, and implantation potential. No clinical decision will be made based upon the resulting Embryo Quality (EQ) Score. The time-lapse based AI software for embryo assessment is an investigational device, which means that it is not approved by the Food and Drug Administration (FDA)

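### oPRP is always given in cycle 2 and the only stated analysis is paired, so the result measures a before-after change; the untreated two-cycle group that could help attribute it is not committed to

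*Protocol*

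**What the plan says.** The order of conditions is the same for everyone. Under Purpose of this Research: "The first cycle will serve as the control (no oPRP treatment), while the second study cycle will incorporate oPRP injections". Sections 2 and 3 of the Study Protocol repeat this order, and the Inclusion Criteria make it a condition of entry: "Willing to undergo two consecutive IVF cycles, with the first cycle serving as a control and the second cycle including oPRP injections".

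The section Number of Subjects / Length of Participation gives the analysis as "Study Design: Self-controlled (paired analysis" and sizes the trial at 180 patients on that comparison. It grants that "we acknowledge the potential for time-dependent confounders and variations in ovarian response". Its only response is the closing sentence: "This study will also consider an external control group of patients undergoing two IVF cycles without oPRP to further validate findings and minimize bias". No size, source, selection rule or role in the analysis follows. The same section schedules an interim analysis at half of enrolment.

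The aim is nevertheless worded causally: "The study will determine if oPRP improves embryo quality and implantation potential". The Primary Outcome Measure is likewise framed as an improvement in blastocyst formation rate after oPRP.

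**The concern.** Treatment and cycle order coincide in every patient. Anything that makes a second cycle differ from a first (experience from cycle 1, a change of laboratory method, the passage of time, selective return after cycle 1) enters the paired difference in full. No later analysis of the paired data alone, in a SAP or elsewhere, can separate it from oPRP. That takes outcomes from patients who had two cycles without oPRP.

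Whether such a group exists is a design decision, and the protocol leaves it open. A group that is only under consideration could also be assembled, or its membership chosen, after the interim or final results are known. At stake is the meaning of the main result. A significant difference would show that cycle 2 did better than cycle 1, not why. A null result could hide a real effect offset by a decline between cycles.

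**Working it through.** **What the comparison estimates.** Let T be the oPRP effect and C the change from cycle 1 to cycle 2 that would occur without oPRP. The expected paired difference is d = T + C. With a single fixed order, the pairs inform only the sum.

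**Inputs from the protocol** (Number of Subjects / Length of Participation): 25% and 35% blastocyst formation per oocyte retrieved, alpha 0.05, power 80%, 180 patients including 10-15% dropout. This leaves 180 × 0.85 = 153 to 180 × 0.90 = 162 completers, or 180 with no loss.

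**Assumptions:** a two-sided test (sidedness is not stated); McNemar's test with one yes/no pair per patient (no test is named); the discordant proportion ψ, which is mentioned without a value; and the size of C, on which the protocol gives no figure.

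**The plan's own figure.** N = (1.96√ψ + 0.842√(ψ − d²))² / d², with d = 0.10.
- Independent cycles: ψ = 0.25×0.65 + 0.35×0.75 = 0.425, giving N = 332.
- 180 evaluable patients correspond to ψ = 0.232, 162 to 0.209, and 153 to 0.198.

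So 180 cannot be reproduced without ψ, but ψ between 0.198 and 0.232 matches the stated 80% power. That range is used below.

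**Effect of a cycle shift.** P(significant in favour of cycle 2) = Φ((d√n − 1.96√ψ) / √(ψ − d²)).
- T = 0, C = +0.05, n = 153, ψ = 0.198: (0.618 − 0.872)/0.442 = −0.57, giving 28%.
- The same with n = 180, ψ = 0.232: (0.671 − 0.944)/0.479 = −0.57, giving 28%. The nominal rate in this direction is 2.5%.
- T = +0.10, C = −0.05: d is again 0.05, so power falls from 80% to 28%.
- T = 0, C = +0.10: d = 0.10, so the test is significant 80% of the time, exactly as for a true 10-point oPRP effect.

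**Sensitivity to the outcome model.** With ψ = 0.425, a +5-point shift gives 16% (n = 153) to 18% (n = 180). With the rate treated as continuous and an assumed SD of change of 0.30, Φ(0.05√n/0.30 − 1.96) gives 54% (n = 153) to 61% (n = 180). The 28% is one illustration within a wide spread.

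**What an external comparison could deliver.** Take 153 per group and a 10-point difference. For unadjusted change, SE = SD × √(2/153) and power = Φ(0.10/SE − 1.96).

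| Assumed SD of change | SE | Power |
|---|---|---|
| 0.30 | 0.034 | 83% |
| 0.44 (ψ = 0.20: √(0.20 − 0.01)) | 0.050 | 51% |
| 0.64 (ψ = 0.425: √(0.425 − 0.01)) | 0.074 | 27% |

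Adjusting for the cycle-1 rate reduces the residual SD to SD × √((1 + ρ)/2), where ρ is the correlation between cycles. At SD 0.64 and ρ = 0 this is 0.455, giving 48% power. Even with unlimited external patients the SE cannot fall below 0.455/√153 = 0.0368, so power stays at Φ(0.10/0.0368 − 1.96), just under 78%. No number of external patients reaches 80% in that case.

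**The case against.** The protocol is open about much of this. It calls the design non-randomized and self-controlled, names time-dependent confounding, and names the right comparator. Section 3 holds trigger thresholds and retrieval constant, and the fertilization method too with one exception: "Fertilization methodology will be identical to the first cycle unless no fertilization is identified in the first cycle". Selection rules, covariates and models commonly belong in a SAP, which may exist. The purpose sentence states an objective, concerns embryo quality and implantation potential rather than the primary blastocyst rate, and stands beside more cautious wording about evaluating whether oPRP helps.

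Most of that is fair. The missing model detail is not the complaint, and neither is the choice of a non-randomized design. What stands is that acknowledging confounding does not control it, that a SAP cannot create a comparator the design has not committed to, and that the primary outcome is also framed as improvement after oPRP.

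The size of any shift is likewise unsupported by the document. The one route that can be sized from the text, the fertilization exception, is small. If patients with no fertilization in cycle 1 rise from 0 to at most 25%, each 1% of such patients adds at most 0.25 points. At an assumed 2-5% of patients that is 0.5 to 1.25 points, and a 3.1-5.6% chance of a false favourable result.

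A reader might also infer that patients enter because cycle 1 went badly, so that regression to the mean guarantees a better cycle 2. The documents do not support this: enrolment and consent to both cycles precede cycle 1. Selective dropout after cycle 1 remains possible, but its direction and size are unknown.

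**Conclusion.** The point holds as a limit on attribution. As written, the trial estimates a change from a first cycle without oPRP to a second with it, and the protocol does not commit to the comparison needed to credit that change to oPRP. This follows from the fixed order and does not depend on any assumed number.

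The 28% figures rest on an assumed 5-point shift, one binary pair per patient, a two-sided test and the discordance implied by the stated power. They show that a moderate shift would matter; they are neither a bound nor an estimate of this trial's error rate. It would go too far to infer that an observed improvement would be an artefact, or that the bias must favour oPRP: the documents give no cycle-to-cycle change without oPRP, and it could go either way. The trial can proceed, but the comparator and the wording of the conclusion should be settled before outcomes are seen.

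**What to change.** In Number of Subjects / Length of Participation, replace the sentence on the external group with:

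> Before any study outcome data are reviewed, including the interim analysis, the rule selecting an external group of clinic patients with two consecutive IVF cycles without oPRP will be fixed. Cycle-2 blastocyst rate per oocyte retrieved will be compared between study and external patients, adjusted for cycle-1 rate, age, AMH, AFC and fertilization method, using a blastocyst count available from the same source in both groups, and reported with a 95% interval as supportive evidence. The paired test will be reported as a before-after change, not by itself as an effect of oPRP. If no suitable external group can be assembled, the conclusion is limited to a before-after change.

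Reword the purpose statement to match. Three details need care:
- The selection rule needs ovarian reserve limits that can be applied to records, because the Inclusion Criteria ask for adequate reserve without a cut-off.
- The primary outcome is assessed by time-lapse with AI, which external patients may not have had; hence the requirement for a common source.
- Study patients receive free ICSI and discounted sperm selection (Compensation for Participation), so fertilization methods may differ between groups; hence that adjustment.

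**Cost.** Records extraction, one more model and a more modest claim. Clinic volume is not given, so the number of eligible external patients is unknown. The comparison is not powered by design: 27-51% unadjusted with 153 per group at an SD of change of 0.64-0.44, and 83% only at 0.30. Selection remains, because external patients did not commit to two cycles in advance and may have returned after a poor first cycle. The result can therefore only be supportive. The fallback costs wording alone.

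Separately, the basis of the cycle-2 stimulation protocol must be reconciled. Purpose of this Research describes "individualized ovarian stimulation protocols based on AMH, AFC and patient history and prior IVF outcomes when applicable" for cycle 1 and applies the same criteria again to cycle 2, section 2 refers to AFC and hormonal profile, and section 3 says the protocol is kept the same.
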